
6. STUDY OBJECTIVES

The primary objective of this study is:

- To assess the effect of 2 dose levels of TMX-049 on urinary albumin excretion in subjects with Type 2 diabetes and albuminuria (a UACR 200 to 3000 mg/g and an eGFR ≥ 30 ml/min/1.73m²). Effects of each TMX-049 dose on UACR will be assessed in terms of ratios using log-transformed UACR at Baseline and after a 12-week period of treatment

The secondary objectives of this study are:

- To assess the effect of each dose of TMX-049 on eGFR during the 12-week period of treatment
- To determine the percentage of subjects with >30% decrease in UACR with placebo and each dose of TMX-049 after 12 weeks of treatment
- To assess the effect of each dose of TMX-049 on exploratory renal biomarkers during the 12-week period of treatment
- To assess the effect of each dose of TMX-049 on sUA during the 12-week period of treatment
- To assess the PK of TMX-049 in subjects with Type 2 diabetes and albuminuria
- To assess safety and tolerability of TMX-049

7. INVESTIGATION PLAN

7.1 Overall Study Design and Plan Description

This will be a randomized, placebo-controlled, double-blind, multicenter, Phase 2 study in subjects with Type 2 diabetes, UACR 200 to 3000 mg/g and eGFR ≥ 30 ml/min/1.73m².

Potentially eligible subjects will attend an initial Screening Visit (Visit 1) and sign an informed consent document. After the subject's medical history is reviewed and inclusion/exclusion criteria for the trial assessed, urine and blood samples will be obtained and sent to a [REDACTED].

Subjects who have a UACR 200 to 3000 mg/g and eGFR ≥ 30 ml/min/1.73m² and meet all other protocol-specified eligibility criteria at Visit 1 will return for Visit 2. At Visit 2, subjects will have a physical examination including triplicate blood pressure measurements, a standard 12-lead ECG, provide blood samples for repeat eGFR, and submit 2 consecutive day mid-stream first-morning void urine samples for Baseline UACR determination for confirmation of eligibility. Subjects will be given study medication to be used during a single-blind, placebo run-in phase and instructed to return their study medication to the site at Visit 3. All pre-randomization study visits will be completed in ≤ 6 weeks. Study medication will be self-administered by the subject qd. Study medication should be taken in the morning at about the same time each day, and taken with food (breakfast or a snack) rather than on an empty stomach beginning on the day after Visit 2.

Subjects who meet all eligibility criteria, including UACR 200 to 3000 mg/g and eGFR ≥ 30 ml/min/1.73m² at both Visit 1 and Visit 2 and who also have $\geq 80\%$ study medication compliance during the 2-week placebo run-in phase, will be randomized at Visit 3 in a 1:1:1 ratio to 1 of 3 treatment groups: placebo, 40 mg of TMX-049, or 200 mg of TMX-049. Approximately 132 subjects will be randomized, with the expectation that 40 subjects per treatment group will complete 12 weeks of treatment and be included in the primary endpoint assessment. Randomization will be stratified by sUA (< 6.0 vs ≥ 6.0 mg/dL) and UACR (200 to < 300 mg/g vs 300 to ≤ 3000 mg/g) levels obtained at Visit 2. Study medication will be self-administered by the subject qd in the morning at about the same time each day and taken with food (breakfast or a snack), rather than on an empty stomach during the randomized treatment phase beginning on the day after Visit 3 and continued until the morning prior to Visit 6. The time of dosing and time of any food intake will remain consistent during the period of randomized treatment.

[figure not shown]
Randomized study participants will return to the site after 2 (Visit 4), 6 (Visit 5), and 12 weeks (Visit 6) of double-blind treatment. Study medication compliance will be assessed by pill count at each visit. First-morning void urine samples will be collected on 2 consecutive days prior to each visit. Urine and blood samples for determination of eGFR, sUA levels, and other laboratory tests will be obtained prior to and after initiation of randomized treatment. Results of sUA and UACR will not be reported to Investigators, subjects, and the Sponsor staff during the randomized treatment phase of the study. The time of PK sample acquisition, the time of dosing prior to the PK sample acquisition, and whether the subject took study medication with or without food will be recorded in the appropriate sections of the case report form (CRF) based on verbal communications with the subjects.

At Visit 4, a sample will be obtained prior to TMX-049 dosing (trough sample). At Visit 5, a sample will be obtained 3 ± 1 hours after study medication dosing (t_{max} sample). The timing of dosing can be adjusted to the time of visiting. At Visit 6, a sample will be obtained ≥ 6 hours (the ideal target is ≥ 8 hours) after study medication dosing (elimination phase sample). If subject cannot visit within the time window, a sample will be obtained when the subject visits, even out of the time window. If the trough sample is not obtained at Visit 4, the trough sample should be obtained at Visit 6, instead of the elimination phase sample. If the trough sample is obtained at Visit 4 and t_{max} sample is not obtained at Visit 5, the t_{max} sample should be obtained at Visit 6, instead of the elimination phase sample. Sites have the option to have a study participant return to the site on a separate day to obtain a properly timed Visit 4, 5, or 6 sample for PK analysis.

Safety assessment will be based on clinical laboratory evaluations, vital signs, physical examinations, and 12-lead ECG, which will be obtained prior to and during the period of randomized treatment.

All study participants will attend a Follow-up Visit (Visit 7) 4 weeks after the last dose of study medication. Two consecutive day urine samples for UACR determination will be submitted by all subjects at this final visit. Urine and blood samples for determination of eGFR, sUA levels, and other laboratory safety tests will be obtained at Visit 7 or at Visit 6 (or the Early Termination Visit).

Figure 1: Study Design

7.2 Discussion of Study Design, Including the Choice of Control Groups

A single-blind, 2-week placebo run-in phase will be conducted prior to randomization to study treatment in order to enter only those subjects who can be expected to have an acceptable level of treatment compliance in the randomized treatment phase of the study.

This treatment phase of the study will be double-blind and placebo-controlled in order to avoid bias in the collection and evaluation of data during its conduct. Placebo has been chosen as the control treatment to assess whether any observed effects are treatment related or simply reflect the study conditions.

The aim of the study is to obtain safety, tolerability, and PK data and to assess effects of TMX-049 on UACR in subjects with Type 2 diabetes and albuminuria. The selected doses are anticipated to be reasonably well tolerated by subjects with Type 2 diabetes and albuminuria for the duration of the investigational treatment period.

A 12-week treatment represents an adequate time to permit the assessment of safety and tolerability of TMX-049 as well as a determination of early proof-of-concept therapeutic effect on reducing UACR compared with placebo, while limiting the potential risk associated with a novel investigational drug.

7.3 Selection of Study Population

The study protocol can only fulfil its objectives if appropriate subjects are enrolled. The following eligibility criteria are designed to select subjects for whom protocol treatment is considered appropriate. All relevant medical and non-medical conditions should be taken into consideration when deciding if participation in this study is suitable for a particular subject.

Note: Subjects with exclusionary laboratory tests or other assessments at Visit 1 and/or Visit 2 may have a

single repeat test at the Investigator's discretion.

7.3.1 Inclusion Criteria

To be eligible to participate in the study, subjects must meet the following criteria:

1. Males or females using a highly effective birth control method or not of childbearing potential who are at least 18 years of age at Visit 1
2. Has Type 2 diabetes and has been treated with ≥ 1 glucose-lowering medication for at least 12 months prior to Visit 1
3. Treatment with at least the minimal recommended dose of an angiotensin converting enzyme inhibitor (ACEI) or an angiotensin II receptor blocker (ARB), but not both, for at least 3 months prior to Visit 1, without any adjustments to this therapy for at least 4 weeks prior to the Visit 1
4. Willingness and ability to provide written informed consent prior to any study-related procedures and to comply with all study requirements
5. Urinary albumin-to-creatinine ratio 200 to 3000 mg/g at Visit 1 and Visit 2. The average of the 2 consecutive day mid-stream, first-morning void UACR results will be used at Visit 2
6. Estimated glomerular filtration rate ≥ 30 ml/min/1.73m² (calculated using the Chronic Kidney Disease Epidemiology Collaboration [CKD-EPI] equation) at Visit 1 and Visit 2
7. Compliance (based on pill count) of $\geq 80\%$ during the single-blind, placebo run-in phase of the study

7.3.2 Exclusion Criteria

Subjects who meet any of the following criteria will not be eligible to participate in the study:

1. Investigational drug use within previous 30 days prior to Visit 1
2. History of Type 1 diabetes
3. Women who are breastfeeding
4. History of drug or alcohol abuse within 1 year of Visit 1
5. Treatment with any uric acid-lowering therapy (eg XO inhibitors and uricosuric agents) within 2 weeks of Visit 1
6. Treatment with [REDACTED] from any time after Visit 2
7. Treatment with [REDACTED] from any time after Visit 2
8. Treatment with [REDACTED] from any time after Visit 2
9. Treatment with [REDACTED] from any time after Visit 2

10. Treatment with use of [REDACTED] from any time after Visit 2
11. Treatment with use of [REDACTED] from any time after Visit 2
12. History of intolerance to any XO inhibitor
13. History of a gout flare requiring pharmacologic treatment
14. History or presence of tophaceous gout
15. History of immunosuppressant treatment for any known or suspected renal disorder at any time prior to Visit 1
16. History of a non-diabetic form of renal disease
17. History of hospitalization for treatment of uncontrolled cardiac arrhythmia, unstable angina, myocardial infarction, any arterial revascularization procedure, or heart failure within 3 months of Visit 1
18. History of hospitalization for treatment of a major psychiatric disorder within 5 years of Visit 1
19. History of any cancer with the exception of basal cell carcinoma of skin or in-situ cervical carcinoma within 5 years of Visit 1. Subjects with a history of cancer who have been disease free for more than 5 years prior to Visit 1 do not require exclusion from the trial
20. Positive test for human immunodeficiency virus (HIV), hepatitis B, or hepatitis C at Visit 2
21. Hemoglobin <10.0 g/dL at Visit 1
22. Glycosylated hemoglobin [HbA1c] >11% at Visit 1
23. Alanine aminotransferase or AST >2 x upper limit of normal (ULN) at Visit 1 or Visit 2
24. Serum uric acid <4.0 mg/dL or >10.0 mg/dL at Visit 1 or Visit 2
25. Systolic blood pressure \geq 160 mmHg or diastolic blood pressure \geq 90 mmHg based on average of triplicate measurement at Visit 1 or Visit 2
26. Fridericia-corrected QT interval (QTcF) \geq 450 ms (males) or \geq 470 ms (females) on an ECG obtained at Visit 2
27. Female subjects with positive urinary pregnancy test at Visit 1 or Visit 3
28. Known bilateral clinically relevant renal artery stenosis (>75%)
29. Dialysis for acute renal failure within the previous 6 months prior to Visit 1
30. Renal allograft in place or a scheduled kidney transplant within the next 22 weeks from Visit 1 (being on a waiting list does not exclude the subject)
31. Congenital or acquired solitary kidney
32. Subjects with a clinical diagnosis of heart failure with reduced ejection fraction and persistent

symptoms (New York Heart Association [NYHA] class III-IV) at Visit 1

33. History or presence of any clinical condition which, in the opinion of the Investigator, impedes ability for the subject to complete all study protocol requirements, increases risk of participation, or is not in the best interest of the study participant

7.3.3 Withdrawal of Subjects

7.3.3.1 *Replacement Procedures*

Subjects who are withdrawn or who choose to withdraw from this study will not be replaced.

7.3.3.2 *Guidance to Investigators on When to End Study Treatment Regimen*

Subjects will be withdrawn if any of the following criteria are met:

- subject decision (withdrawal of consent)
- any clinically relevant signs or symptoms that in the opinion of the Investigator warrant subject withdrawal
- ALT or AST >8 x ULN
- ALT or AST >5 x ULN for more than 2 weeks
- ALT or AST >3 x ULN and with either a total bilirubin >2 x ULN or and International Normalized Ratio (INR) >1.5
- ALT or AST >3 x ULN with the appearance of fatigue, nausea, vomiting, right upper quadrant pain or tenderness, fever, rash, and/or eosinophilia (>5%)
- eGFR ≤ 15 ml/min/1.73m², confirmed with repeat measurement
- development of an inter-current illness, condition, or procedural complication that in the opinion of the Investigator would interfere with the subject's continued participation
- development of an intolerable AE as determined by the Investigator and/or subject
- positive pregnancy test result
- significant protocol non-compliance in the study, as considered applicable by the Investigator
- if it becomes necessary to break the blinding code for a subject

A subject is free to withdraw from the study at any time for any reason without prejudice to their medical care. In addition, the Investigator may decide, for reasons of medical prudence, to withdraw a subject. In either event, the Sponsor will be notified and the date and reason(s) for the withdrawal will be documented in the subject's source data. Should the randomization code be broken for a subject, the date, time, and reason will be recorded in the subject's source data.

The Investigator will also withdraw the subject from the study upon the request of the Sponsor or if the Sponsor terminates the study. Upon occurrence of a serious or intolerable AE, the Investigator should confer with the Sponsor before discontinuing the subject.

If a subject has started the investigational medicinal product (IMP) and subsequently develops an inter-current medical problem, the Investigator may decide to withdraw IMP administration temporarily on clinical grounds. If the subject recovers and there are no clinical contraindications to resuming IMP administration this should be allowable within the protocol if the treating clinician feels it is appropriate to do so.

7.3.3.3 Follow-Up of Subjects Prematurely Discontinued from the Study Treatment Regimen or Withdrawn from Study

If a subject is withdrawn or chooses to withdraw, an early termination visit and end of study visit will be performed if possible (see [Table 2](#)). The Investigator may also request that the subject returns for an additional follow-up visit.

Where possible all subjects who discontinue due to AE will be followed up at suitable intervals to evaluate the course of the AE and to ensure reversibility or stabilization. The subsequent outcomes of these events will be recorded on the paper CRF.

If a subject is withdrawn or chooses to withdraw prior to randomization, no additional tests are required.

7.4 Treatment of Subjects

Study medication is defined as any investigational treatment(s) or placebo intended to be administered to a study participant according to the study randomization or treatment allocation.

7.4.1 Treatments Administered

All eligible subjects will receive qd doses of placebo during a 2-week placebo run-in phase. Subjects with $\geq 80\%$ study medication compliance during the 2-week placebo run-in phase will be randomized to receive qd doses of 40 mg TMX-049, 200 mg TMX-049, or placebo during the double-blind 12-week treatment phase.

On each dosing occasion, subjects assigned to the placebo group will swallow 1 tablet (placebo) and 2 capsules (placebo), subjects assigned to the low-dose group (40 mg TMX-049) will swallow 1 tablet (40 mg TMX-049) and 2 capsules (placebo), and subjects assigned to the high-dose group (200 mg TMX-049) will swallow 1 tablet (40 mg TMX-049) and 2 capsules (80 mg TMX-049) with water. All tablets/capsules making up a dose must be taken at the same time (ie dividing a dose is not permitted).

Treatment group	Capsule	Tablet
TMX-049 200-mg group	2 x 80-mg TMX-049 capsules	1 x 40-mg TMX-049 tablet
TMX-049 40-mg group	2 x placebo capsules	1 x 40-mg TMX-049 tablet
Placebo group	2 x placebo capsules	1 x placebo tablet

Subjects will be instructed to take study medication qd in the morning at approximately the same time each day. Subjects should take study medication with food, rather than on an empty stomach whenever possible, although occasional administration on an empty stomach is permissible. Subjects who don't usually eat breakfast should eat something (a snack would be acceptable), prior to dosing. Study medication will begin the morning after Visit 2 in the placebo run-in phase and the morning after Visit 3 at the beginning of the randomized treatment phase. The last dose of study medication will be taken in the morning before Visit 6.

If a subject does not take a dose of study drug within +12 hours of their regular dosing time, then the dose of study drug should be skipped and the subject should be instructed to take the study drug at the next regularly scheduled time. If a dose is missed, the site notified and recorded in the appropriate sections of the CRF based on verbal communications with the subjects. If a subject takes more than the intended dose,

they should report this to the site and an AE will be recorded if there were symptoms that accompanied the additional dose taken.

At Visit 4, subjects should not take study medication in the morning before their visit. Subjects can take study medication after the PK sample is obtained provided it is taken within +12 hours of their regular dosing time.

At Visit 5, subjects should take study medication approximately 3 hours before the visit. Therefore, the time of dosing may not necessarily be in the morning and can be adjusted according to the time of the visit.

At Visit 6, subjects should take study medication in the morning.

The time of PK sample acquisition, the time of dosing prior to the PK sample acquisition and whether the subject took study medication with or without food will be recorded in the appropriate sections of the CRF based on verbal communications with the subjects.

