7.5.4.4 Visit 5: Study Day 42 ± 7 Days

The following information and procedures will be recorded and performed at Visit 5:

- pre-Visit 5 call for reminder of urine collection and dosing approximately 3 hours before the visit before visit
- contact IXRS

- study drug administration; see [Section 7.4.1](#)
- urine sample for UACR (2 consecutive day mid-stream, first-morning void urine samples to be collected at the subject's home on the morning before and the morning of Visit 5)
- complete blood count
- serum chemistry profile (including sUA and serum creatinine to calculate eGFR); see [Appendix A](#) for the evaluations to be performed
- thyroid hormones
- lipid panel
- urinalysis
- blood (plasma and serum) and urine sample for biomarkers (the mid-stream, first-morning void urine samples collected by the subjects at home will be used for the analysis of biomarkers)
- treatment-emergent adverse event recording
- concomitant medication review
- vital signs, consisting of supine blood pressure, supine pulse rate, and oral body temperature
- body weight
- PK sampling, see [Section 7.7.1](#)
- 3 study drug treatment kits will be dispensed to the subject
- dispense urine collection supplies (for collection of 2 consecutive day first-morning void urine samples on the morning before and the morning of the subsequent visit)
- assess double-blind compliance

7.5.4.5 *End of Treatment Visit 6: Study Day 84 ± 7 Days or Early Termination Visit*

The following information and procedures will be recorded and performed at Visit 6:

- contact IXRS
- pre-Visit 6 call for reminder of urine collection, dosing in the morning before the visit
- dispense urine collection supplies (for collection of 2 consecutive day first morning void urine samples on the morning before and the morning of the subsequent visit)
- urine sample for UACR (2 consecutive day mid-stream, first-morning void urine samples to be collected at the subject's home on the morning before and the morning of Visit 6)
- complete blood count
- serum chemistry profile (including sUA and serum creatinine to calculate eGFR); see [Appendix A](#)

for the evaluations to be performed

- thyroid hormones
- lipid panel
- HbA1c
- urinalysis
- urine pregnancy test for female subjects of childbearing potential (only Early Termination Visit)

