7.6.2.6 Clinical Laboratory Evaluations

Blood and urine samples will be collected for clinical laboratory evaluations at the times indicated in the Schedule of Assessments ([Table 2](#)).

Additional clinical laboratory evaluations will be performed at other times if judged to be clinically appropriate or if the ongoing review of the data suggests a more detailed assessment of clinical laboratory safety evaluations is required.

An Investigator will perform a clinical assessment of all clinical laboratory data.

The evaluations to be performed are listed in [Appendix A](#).

The results of UACR and sUA at Visits 3, 4, 5, 6, and 7 will not be reported Investigators, subjects, and the Sponsor staff. Investigators must not measure UACR or sUA at local sites.

7.6.2.7 *Blood Sample for HbA1c*

A blood sample will be collected for the measurement of HbA1c at the times indicated in the Schedule of Assessments (Table 2).

7.6.2.8 *Physical Examinations*

Full physical examinations will be performed at the times indicated in the Schedule of Assessments (Table 2).

7.6.2.9 *Body Weight*

Body weight (in underclothes) will be recorded at the times indicated in the Schedule of Assessments (Table 2). Body weight should be taken at the same time of day, and using the same equipment.

7.7 **Pharmacokinetic Analysis**

7.7.1 **Blood Sampling for the Analysis of Plasma TMX-049**

Blood samples (approximately 1 x 5 mL) will be taken by venipuncture or cannulation at the times indicated in the Schedule of Assessments (Table 2).

Samples taken from subjects in placebo group will not be analyzed.

At Visit 4, a sample will be obtained prior to TMX-049 dosing (trough sample).

At Visit 5, a sample will be obtained 3 ± 1 hours after study medication dosing (t_{max} sample). The timing of dosing can be adjusted to the time of visiting.

At Visit 6, a sample will be obtained ≥ 6 hours (the ideal target is ≥ 8 hours) after study medication dosing (elimination phase sample).

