If a subject cannot visit within the time window, a sample will be obtained when the subject visits, even out of the time window. If the trough sample is not obtained at Visit 4, the trough sample should be obtained at Visit 6, instead of the elimination phase sample. If the trough sample is obtained at Visit 4 and t_{max} sample is not obtained at Visit 5, the t_{max} sample should be obtained at Visit 6, instead of the elimination phase sample. Sites have the option to have a study participant return to the site on a separate day to obtain a properly-timed Visit 4, 5, or 6 sample for PK analysis.

The time of PK sample acquisition, the time of dosing prior to the PK sample acquisition and whether the subject took study medication with or without food will be recorded in the appropriate sections of the CRF based on verbal communications with the subjects.

██████████ will be responsible for the analysis of plasma TMX-049. Aliquots of plasma will be stored for potential use in possible future exploratory PK assays.

7.7.2 **Population Pharmacokinetic Analysis**

The sparse samples collected will be included into a population PK analysis.

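### Moving a missed Visit 4 trough sample to Visit 6 has no matching hold-dose instruction, so a subject who doses as told before Visit 6 cannot provide it

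*Protocol*

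**What the plan says.** Protocol 7.7.1 fixes what a trough is: "At Visit 4, a sample will be obtained prior to TMX-049 dosing (trough sample"). It then gives the fallback for when that draw is missed: "the trough sample should be obtained at Visit 6, instead of the elimination phase sample". The same fallback stands in the synopsis, Protocol 7.1, footnote 10 of Table 2, SAP 2.2 and the schedule reproduced at the end of the SAP.

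The dosing rules are in Protocol 7.4.1. The Visit 4 rule is a hold: "At Visit 4, subjects should not take study medication in the morning before their visit". A further sentence lets the held dose be swallowed once blood has been drawn, up to 12 hours late. The Visit 4 reminder call in 7.5.4.3 repeats the hold. For Visit 6, 7.4.1 says "At Visit 6, subjects should take study medication in the morning". An earlier paragraph of the same section fixes the final dose in like terms: "The last dose of study medication will be taken in the morning before Visit 6". The Visit 6 procedures in 7.5.4.5 list a "pre-Visit 6 call for reminder of urine collection, dosing in the morning before the visit". None of the three Visit 6 lines carries an exception.

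Sites may bring a subject back on a separate day for a properly timed sample from Visit 4, 5 or 6. Samples outside the window are still drawn, and dose and sample times are recorded.

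**The concern.** Dosing is at home, and the Visit 6 lines put the dose before the subject reaches the site. A subject who missed the Visit 4 trough and does as the reminder call says arrives already dosed, so the sample that the fallback asks for can no longer be taken at that visit. The protocol evidently regards a written hold as necessary, because it gives one for Visit 4 in both 7.4.1 and the call. The relocated trough has a sampling rule but no dosing rule.

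At stake is trough information for the PK objective, which is secondary. Each subject has three planned PK samples, one of which is a trough.

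**Working it through.** The documents state no figure to reproduce. The check is to set the instructions side by side, with a little arithmetic for size and timing.

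**Instructions by visit**

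| | Visit 4 (trough) | Visit 6 (default: elimination sample) | Visit 6 (trough moved there) |
|---|---|---|---|
| Sample required | before dosing | at least 6 h after dosing, ideally at least 8 h | before dosing |
| Dosing line in 7.4.1 | hold, then dose after the draw | dose in the morning, before the visit | none of its own; the default applies |
| Reminder call | do not dose | dose before the visit | none of its own; the default applies |

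The first two columns are consistent. In the third, the sample must be pre-dose and the only written dosing instruction makes it post-dose.

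**Readings that might remove the conflict**

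- "At Visit 6, subjects should take study medication in the morning" alone would allow an early appointment, a draw and then the morning dose. "The last dose of study medication will be taken in the morning before Visit 6" and the reminder call close that reading.
- The synopsis, 7.1 and SAP 2.2 have dosing continue to the morning prior to Visit 6, which could mean the previous day. That contradicts 7.4.1 and 7.5.4.5. It would also put the planned elimination sample about a day after dosing, so that exchanging it for a trough would change nothing.
- The sentence allowing dosing to be adjusted to the visit time belongs to Visit 5.

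**Size**

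- Randomized (Protocol 7.10.1): 132 / 3 = 44 per group, so 2 x 44 = 88 on TMX-049.
- Expected to complete 12 weeks (Protocol 7.1): 40 per group, so 2 x 40 = 80 on TMX-049. This is the closer denominator for a Week 12 Visit 6.
- Affected: from 0, if every site reads the fallback as overriding the dosing line, up to the active-arm subjects at Visit 6 whose missed Visit 4 trough was not recovered on another day. The documents give neither a miss rate nor a recovery rate.
- Loss per affected subject: the single planned trough. A Visit 6 sample is still obtained.

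**Why the post-dose sample does not replace the trough (illustration)**

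Assume a single-exponential decline, a true trough at 24 h, and the half-life range of 10 to 19 h in Protocol 5.4.3. The ratio of a sample at h hours to the trough is 2^((24 - h) / half-life).

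- h = 6: 2^(18/19) = 1.9 to 2^(18/10) = 3.5
- h = 8: 2^(16/19) = 1.8 to 2^(16/10) = 3.0

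Protocol 5.4.3 describes the decline as biphasic, so these ratios are approximate.

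**Timing if the dose is held**

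If the appointment stays at the time meant for the elimination sample, the draw falls at least 24 + 6 = 30 h after the previous dose, or at least 24 + 8 = 32 h at the ideal target. The +12 hour allowance then has at most 12 - 6 = 6 h, or 12 - 8 = 4 h, left. The elimination window has no upper limit, so the first pair are minima and the second maxima.

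**The case against.** The best defence is that ordinary reading resolves this. The fallback is specific and conditional, a trough is pre-dose by definition, and the Visit 6 dosing lines exist to serve the elimination sample that the fallback replaces. On that reading, obeying the fallback implies holding the dose. Investigators give the intake instructions (Protocol 7.4.2.2), and the reminder call may cover dosing (7.5.4.1), so a hold message could be delivered. This stands as far as it goes, and it is why the lower bound is zero. But these provisions permit a hold without supplying one, the text gives neither rule priority, and the listed call prompts the subject to dose.

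A second defence is recovery. A missed Visit 4 trough can be redrawn on a separate day without waiting for Visit 6. That also stands and shrinks the affected group, but the return is optional.

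A third is that little is lost, and this largely stands. The missed Visit 4 draw is the root cause; the wording forfeits only the substitute. The subject still gives a post-dose sample, normally the one first planned for Visit 6. The SAP's PK endpoint is concentration by visit, summarized descriptively without formal tests, and nothing in it depends on a trough. The PK Population asks only for a dose of TMX-049 and evaluable PK data.

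**Conclusion.** The point holds as a minor wording inconsistency. The relocated trough cannot be obtained at Visit 6 from a subject who follows the written Visit 6 dosing instructions and reminder call. Such a subject, unless recovered on a separate day, finishes without a trough but with a post-dose sample whose timing is known. The number is unknown and may be zero; the pool is the roughly 80 active-arm subjects expected to complete 12 weeks.

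A reader might infer more than this:

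- **That the population PK analysis is biased.** The documents do not support this. Actual dose and sample times are recorded, so a post-dose sample can enter the model at its true time.
- **That all 88 randomized active-arm subjects are exposed.** Only those who missed the Visit 4 trough and were not recovered are exposed, and 88 includes subjects expected to leave before Week 12.
- **That efficacy or safety conclusions suffer.** Neither uses the trough sample.

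The conclusion rests on reading the Visit 6 lines as a dose on the day of the visit, before arrival, which is what 7.4.1 and 7.5.4.5 say together.

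**What to change.** In Protocol 7.4.1 and the pre-Visit 6 call in 7.5.4.5, state that any subject, in any arm, without a Visit 4 trough holds the Visit 6 dose until the PK sample is drawn and may then dose within 12 hours after the regular time, as at Visit 4. All other subjects dose in the morning as now. Unused drug is returned at Visit 6 and none is dispensed there (7.4.2.1, Table 2), so add that the held dose comes from the subject's own wallet before it is collected. Add an exception for a trough moved to Visit 6 to the last-dose lines in the synopsis, 7.1 and SAP 2.2.

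Book these subjects early, near 24 hours after the previous dose, to avoid a draw at 30 hours or later.

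The cost is a per-subject flag for the outstanding sample and a delayed final dose in flagged subjects, whose other Visit 6 blood samples would then also be pre-dose. The flag must run in all three arms, although placebo PK samples are not analyzed, because sites are blinded. No extra visit or sample is needed.
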